13.3 Disease History

Information on disease history collected prior to dosing is found on the "Disease History" eCRF. The following will be summarized:

- Site of primary tumor at study entry
- Time since first occurrence of metastatic or locally advanced disease (months) defined as (the first trial treatment date the date of first occurrence of metastatic or locally advanced disease) / 30.4375
- Time since initial diagnosis (years) defined as (the first trial treatment date the date of initial diagnosis) / 365.25Root cause of HCC as assessed by investigator: Hepatitis B virus (HBV), Hepatitis C virus (HCV), alcohol induced cirrhosis, other
- Tumor, lymph nodes, metastasis (TNM) classification at initial diagnosis
- TNM classification at study entry
- Tumor Histology
 - o Macroscopic Category (Massive/Nodular/Diffuse/Other)
 - Microscopic Category (Trabecular/Pseudoglandular/Compact/Scirrous/ Fibrolamellar/Clear Cell/Sclerosing/Sarcomatoid/Inflammatory HCC or Lympho-Epithelial-Like Carcinoma/Other)
 - Vascular Invasion (Yes/No/Not Available)
 - o Grading (1/2/3/4/Not Available)

A listing of disease history will be provided with all relevant data (as collected on the "Disease History" eCRF page) and derived variables used in the above summary table.

13.4 Other Baseline Characteristics

The following baseline characteristics will be reported for this study:

- Height (cm) (collected on the "Vital Signs" eCRF page)
- Weight (kg) (collected on the "Vital Signs" eCRF page)
- Body Mass Index (kg/m²) (derived as indicated below)
- ECOG PS: 0 or 1 (collected on the "ECOG Performance Status" eCRF page)
- FHSI-8 score (collected on the "FHSI-8" eCRF page)
- Functional Assessment of Cancer Therapy-Hepatobiliary (FACT-HP) score (collected on the "FACT-HP" eCRF page)

- Nicotine use status: Never used, Regular user, Occasional user, or Former user (collected on the "Nicotine Consumption" eCRF page)
- Alcohol use: Yes or No (collected on the "Alcohol Consumption" eCRF page)
- AFP elevation at baseline: ≥ 200 IU/mL or < 200 IU/mL (collected on the "Tumor Markers" eCRF page)
- Prior local-regional therapy: Yes or No (collected on the "Prior Anti-Cancer Local-Regional Therapy" eCRF page)
- Albumin-Bilirubin (ALBI) Grade (1): 1, 2, or 3 (derived as indicated below)

Specifications for computation:

- ALBI Grade (1):
 - O Calculate the linear predictor y: $y = (log_{10}(bilirubin) * 0.66) + (albumin * -0.085)$ where bilirubin is in μ mol/L and albumin is in g/L
 - o Compare y to the following cut points:
 - ALBI Grade 1: $y \le -2.60$
 - ALBI Grade 2: $-2.60 < y \le -1.39$
 - ALBI Grade 3: y > -1.39
- Body mass index (kg/m^2) = weight $(kg)/[height (m)]^2$

13.5 Baseline Biomarkers in Tumor

The following baseline biomarkers will be reported for this study:

- c-Met Status: Immunohistochemistry (IHC) 0, IHC 1+, IHC 2+, IHC 3+ (collected as part of the immunology data at Q² Solutions, defined as indicated below)
- c-Met Status: In Situ Hybridization (ISH): ISH+, ISH- (derived as indicated below)
- Cancer-Associated Fibroblast (CAF) HGF Immunohistochemistry (IHC) (collected as part of the immunology data at Q² Solutions, defined as indicated below)
- Cytoplasmic HGF: Immunohistochemistry (IHC) (collected as part of the immunology data at Q² Solutions, defined as indicated below)

Specifications for computation:

• c-Met Status (IHC)

- IHC 0: No staining of tumor cells, or < 50% of tumor cells with membrane and/or cytoplasmic staining of any staining intensity (or combination of intensities)
- o IHC 1+: ≥ 50% of tumor cells with at least weak (1+) membrane and/or cytoplasmic staining, but < 50% of tumor cells with moderate or strong membrane and/or cytoplasmic staining
- o IHC 2+: ≥ 50% of tumor cells with at least moderate (2+) membrane and/or cytoplasmic staining, but <50% of tumor cells with strong membrane and/or cytoplasmic staining
- o IHC 3+: \geq 50% of tumor cells with strong (3+) membrane and/or cytoplasmic staining with strong intensity
- c-Met Status (ISH):
 - ISH+ if a subject has a mean gene copy number \geq 5 or a MET:CEP7 ratio \geq 2
 - o ISH- if a subject has a mean gene copy number < 5 and a MET:CEP7 ratio < 2
 - o For ISH+ cases, the mean gene copy number and the ratio should be reported
- CAF HGF (IHC):
 - Histo-score of expression with range (1-300)
- Cytoplasmic HGF (IHC):
 - Histo-score of expression with range (1-300)

Baseline biomarker status/values will be summarized using descriptive statistics in a frequency table. The correlation/association between c-Met expression (IHC) and amplification (ISH) status will be analyzed by presenting a cross-tabulation table.

Moreover, the demographics table will be repeated with the following baseline biomarker groups as to investigate distribution of demographic data in the baseline biomarker groups:

- table by baseline IHC group [IHC 0, IHC 1+, IHC 2+, IHC 3+]
- table by baseline ISH group [ISH+, ISH-]

13.7 Prior Anti-Cancer Therapies

Information related to prior anti-cancer therapies were collected on the "Prior Anti-Cancer Drug Therapies Details", "Prior Anti-Cancer Radiotherapy Details", "Prior Anti-Cancer Local-Regional Therapy Details", and "Prior Anti-Cancer Surgery Details" eCRF pages.

The number of subjects in each of the following anti-cancer therapy categories will be tabulated:

• Subjects with at least one type of prior anti-cancer treatment

- Subjects with at least one prior anti-cancer drug therapy
- Subjects with at least one prior anti-cancer radiotherapy
- Subjects with at least one prior anti-cancer local-regional therapy
- Subjects with at least one prior anti-cancer surgery

Prior anti-cancer drug therapy will be summarized as follows:

- Number of subjects with at least one prior anti-cancer drug therapy
- Number of any prior anti-cancer therapy regimens: missing $/ 1 / 2 / 3 / \ge 4$
- Number of prior anti-cancer drug therapy for metastatic/locally advanced disease: missing $/ 1 / 2 / 3 / \ge 4$.
- Type of prior anti-cancer therapy: Cytotoxic Therapy / Endocrine Therapy / Monoclonal Antibodies Therapy / Small Molecules / Immunotherapy / Other
- Intent of Therapy: Neo-Adjuvant / Adjuvant / Metastatic or Locally advanced
- Best response: Complete Response (CR) / Partial Response (PR) / Stable Disease (SD) / Progressive Disease (PD) / Not-Complete Response/Non-Progressive Disease (Non-CR/non-PD) / Not assessable / Unknown. Best response is derived from the last treatment regimen

The prior anti-cancer drugs will also be extensively detailed with the number and percentage of subjects by the drug class and PT in a table. A subject will be counted only once within a given drug class and within a given drug name, even if he/she received the same medication at different times. The summary will be sorted on decreasing frequency of drug class and decreasing frequency of drug name in a given drug class. In case of equal frequency regarding drug class (respectively drug name), alphabetical order will be used.

Listings of prior anti-cancer treatments and procedures will also be provided: a) listing of prior anti-cancer drug therapies, b) listing of prior anti-cancer radiotherapy, c) listing of prior anti-cancer local-regional therapy and d) listing of prior anti-cancer surgeries. These will include the subject identification number, and all the relevant collected data-fields on the corresponding eCRF pages. Prior anti-cancer drug therapies will be coded using the World Health Organization Drug dictionary (WHO-DD).

14 Previous or Concomitant Medications/Procedures

Analysis Set: ITT/SAF

14.1 Prior and Concomitant Medications/Procedures

Concomitant treatments are medications, other than trial medications, taken by subjects any time during the on-treatment period.

Previous medications are medications, other than trial medications and pre-medications for trial treatment, which are started before first administration of trial treatment.

Previous and concomitant medications will be summarized from the "Concomitant Medications Details" eCRF page.

In cases where date values do not allow unequivocal allocation of a medication to concomitant or previous medication, the medication will be considered as both a concomitant and previous medication. Incomplete concomitant or previous medication-related dates will be handled as described in section 17.1.

Summaries of previous and concomitant medications will include the number and percentage of subjects by Anatomical Therapeutic Chemical (ATC) classification level 2 and PT, as given from the latest version of the WHO-DD. A subject will be counted only once within a given ATC class and within a given PT, even if he/she received the same medication at different times. If any previous or concomitant medication is classified into multiple ATC classes, the medication will be summarized separately under each of these ATC classes. Summary tables will be sorted alphabetically by ATC class and PT. In case any specific medication does not have an ATC classification level 2 coded term, it will be summarized under the "Unavailable ATC classification" category.

A listing of previous and concomitant medications will be created with the information collected on the "Concomitant Medications Details" eCRF page.

All **concurrent procedures**, which were undertaken any time on trial, were collected on the eCRF page "Concomitant Procedure Details". The number and percentage of subjects with any concurrent procedure, a concurrent procedure starting prior to the first dose of treatment, and a concurrent procedure starting after the start of treatment but within 33 days after the last dose of trial treatment will be presented.

A listing of concurrent procedures will be created with the information collected on the "Concomitant Procedures Details" eCRF page.

14.2 Subsequent Anti-Cancer Therapies/Procedures

Anti-cancer treatment after discontinuation will be provided in a data listing with data retrieved from "Anti-Cancer Treatment After Discontinuation Details", "Anti-Cancer Radiotherapy After Discontinuation", and "Anti-Cancer Surgeries After Discontinuation" eCRF pages.

15 Treatment Compliance and Exposure

Analysis Set: ITT/SAF

All dosing calculations and summaries will be based on the "MSC2156119J Administration Details" eCRF page.

Handling of missing data:

If the actual dose is missing, the planned dose level as entered in the eCRF will be used.

Cumulative Dose

The cumulative dose (mg) of tepotinib per subject is the sum of the actual dose levels that the subject received (i.e. total dose administered [mg]).

Duration

For the purposes of deriving dose intensity, the duration of therapy (in weeks) during the trial is defined as:

Duration
$$\left(\frac{\text{last dose date first dose date} + 1}{7}\right)$$

The duration of therapy (in months) during the trial is defined as:

Duration
$$\left(\frac{\text{last dose date first dose date} + 1}{30.4375}\right)$$

Dose Intensity

The dose intensity and the relative dose intensity will be calculated for each subject across all cycles assuming a 3-week cycle duration. Dose intensity (mg/cycle) is defined as

Dose intensity
$$\left(\frac{\text{Cumulative dose}}{(\text{duration of therapy (in weeks)})/3}\right)$$

Relative Dose Intensity

Relative dose intensity, a measure of compliance, is defined as the dose intensity divided by the planned dose per cycle.

Number of Cycles Completed

The number of cycles a subject completed will be calculated as follows:

Number of cycles completed floor
$$\left(\frac{\text{(last dose date - first dose date + 1)}}{21}\right)$$

Number of Cycles Initiated

The number of cycles a subject initiated will be calculated as follows:

Number of cycles initiated ceiling
$$\left(\frac{\text{(last dose date - first dose date + 1)}}{21}\right)$$

The following will be summarized:

- Total number of initiated vs. completed cycles on treatment
- Duration (months)
- Cumulative dose (mg)
- Dose intensity (mg/cycle)
- Relative dose intensity (%)

Listings of treatment exposure and compliance will be created to present the information listed above for each subject.

Dose reductions

A dose reduction is defined as a change from the planned dose level to one of the 2 lower dose levels below the RP2D (See CTP Section 6.2.3). The number of subjects with at least one dose reduction will be summarized by frequency and percentage. The minimum dose of the trial treatment will be derived per subject and categorized as reduced to 300 mg or reduced to 200 mg.

Dosing interruptions

A dose interruption is defined as having missed 1 or more planned daily doses. Dosing interruptions will be summarized by planned dose level for the number of subjects with an interruption lasting either 1-2 days, 3-7 days, 8-14 days, and greater than 14 days (The longest interruption and cumulative days of interruption are summarized for each subject.)

Investigational Medicinal Product (IMP) Allocation

A listing of batch numbers of IMP and the subjects receiving IMP from the specific batch will be presented.

16 Endpoint Evaluation

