# 6.2 Dosage and Administration

For each dose cohort, a fixed dose and administration will be applied. The assigned dose of MSC2156119J will be administered daily, using the appropriate number of 25 mg and/or 100 mg film-coated tablets.

Subjects will take their assigned doses of MSC2156119J orally once daily, in the morning at approximately the same time each day ( $\pm$  2 hours), immediately after breakfast, with a full glass of water (approximately 200 mL), every day of each 21 day treatment cycle until the determination of PD (as assessed by the investigator according to RECIST Version 1.1), intolerable toxicity, or withdrawal from the trial.

Subjects will be instructed to swallow the tablets wholly and to avoid biting or breaking the tablets, or attempting to dissolve in water before taking the dose.

On days when PK samples are to be drawn, subjects should be instructed to attend the trial visit in a fasted state, with no breakfast and prior to taking their dose of MSC2156119J. After a predose PK blood sample is drawn, the assigned dose of MSC2156119J should be taken following breakfast. No further food should be consumed until 2 hours after the dose (water is allowed).

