# 6.2.3 Dose Adjustments and Missed Doses

If a dose is missed during breakfast, subjects will be instructed to take it immediately with food before the end of day.

As for dose adjustment, subjects will remain on their starting dose of MSC2156119J throughout the trial with the exception of dose modification due to tolerability (applicable for both Phase Ib and Phase II).

Subjects who miss more than ~20% of doses planned during Cycle 1 (i.e., 4 days) for reasons other than adverse drug reactions or DLTs will not be evaluable for the assessment of the primary endpoints of Phase Ib.

Subjects are permitted to have dose modifications to ensure the MSC2156119J is well tolerated at the scheduled dose levels. A two-level dose schedule is applied for dose modification, i.e., the next 2 lower levels than RP2D. If a subject still does not tolerate the permitted lowest dose, the subject will be withdrawn from the trial. Assuming that the RP2D is 500 mg daily, the next 2 lower dose strengths to adjust to in case of toxicity would be 300 mg and then 200 mg. The maximum permitted dosing delay is 21 days.

AEs assessed by the investigators to be exclusively related to the subject's underlying disease or medical condition/concomitant treatment are not applied for the guideline of dose modification.

The following dose modification guideline for MSC2156119J is recommended. However the investigators could otherwise modify the dosage based on clinical circumstances on a case-by-case basis. Under such circumstance, the investigators should notify the sponsor case by case and provide the reason to the sponsor.

Under the following circumstances, the dose should be interrupted temporarily until AEs recover to Grade 1 (or less) or baseline. Subjects can be rechallenged at the next lower dose level; the dose should be temporarily discontinued on the first day of occurrence of the following AEs:

- Grade 4 neutropenia for more than 7 days
- Grade  $\geq$  3 febrile neutropenia for more than 1 day
- Grade 4 thrombocytopenia or Grade 3 thrombocytopenia with bleeding
- Grade ≥ 3 uncontrolled nausea/vomiting and/or diarrhea despite adequate and optimal treatment for more than 3 days
- Grade ≥ 3 any nonhematological AE, except the aforementioned gastrointestinal events and alopecia; however, the following cases are specifically defined:
  - $\circ$  Grade  $\geq$  3 liver AE requiring a recovery period of more than 7 days to the baseline or to Grade 1 or less

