All dosing calculations and summaries will be based on the "Cohort Treatment MSC2156119J Administration Details" eCRF page.

Handling of missing data:

If the actual dose is missing, the planned dose level as entered in the eCRF will be used.

Cumulative Dose

The cumulative dose (mg) of tepotinib per subject is the sum of the actual dose levels that the subject received (i.e. total dose administered [mg]).

Duration

For the purposes of deriving dose intensity, the duration of therapy (in weeks) during the trial is defined as:

Duration=
$$\left(\frac{\text{last dose date - first dose date} + 1}{7}\right)$$

The duration of therapy (in months) during the trial is defined as:

Duration=
$$\left(\frac{\text{last dose date - first dose date} + 1}{30.4375}\right)$$

Dose Intensity

The dose intensity and the relative dose intensity will be calculated for each subject across all cycles assuming a 3-week cycle duration. Dose intensity (mg/cycle) is defined as

Dose intensity=
$$\left(\frac{\text{Cumulative dose}}{(\text{duration of therapy (in weeks)})/3}\right)$$

Relative Dose Intensity

Relative dose intensity, a measure of compliance, is defined as the dose intensity divided by the planned dose per cycle.

Number of Cycles Completed

The number of cycles a subject completed will be calculated as follows:

Number of cycles completed = floor
$$\left(\frac{\text{(last dose date - first dose date + 1)}}{21}\right)$$

Number of Cycles Initiated

The number of cycles a subject initiated will be calculated as follows:

Number of cycles initiated = ceiling
$$\left(\frac{\text{(last dose date - first dose date + 1)}}{21}\right)$$

The following will be summarized:

- Total number of initiated vs. completed cycles on treatment
- Duration (months)
- Cumulative dose (mg)
- Dose intensity (mg/cycle)
- Relative dose intensity (%) during Cycle 1 and overall

Dose reductions

A dose reduction is defined as a change from the planned dose level to one of the 2 lower dose levels below the recommended phase II dose (RP2D) (See CTP Section 6.2.3). The number of subjects with at least one dose reduction will be summarized by frequency and percentage per planned dose level. The minimum dose of the trial treatment will be derived per subject and categorized according to categories of reduced to 300 mg and reduced to 200 mg.

Dosing Interruptions

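### Both SAPs count a dose reduction only when it reaches one of two scheduled levels, so a subject lowered only to another dose under the protocol's case-by-case clause is missing from the reduction table

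*SAP*

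**What the plan says.** **Phase II SAP, section 15 (Dose reductions).** The definition is "A dose reduction is defined as a change from the planned dose level to one of the 2 lower dose levels below the RP2D", with a reference to protocol 6.2.3. Subjects with at least one reduction are then counted, and "The minimum dose of the trial treatment will be derived per subject and categorized as reduced to 300 mg or reduced to 200 mg". There is no other category.

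**Phase Ib SAP, section 15 (Dose reductions).** The definition is the same and the count is given per planned dose level. On categories: "The minimum dose of the trial treatment will be derived per subject and categorized according to categories of reduced to 300 mg and reduced to". The second category, which closes that sentence, is again 200 mg.

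**Protocol 6.2.3.** The schedule is "A two-level dose schedule is applied for dose modification, i.e., the next 2 lower levels than RP2D". On the working assumption of a 500 mg RP2D, "the next 2 lower dose strengths to adjust to in case of toxicity would be 300 mg and then 200 mg". A guideline listing the adverse events that call for interruption and rechallenge follows. It is introduced as recommended and qualified by: "However the investigators could otherwise modify the dosage based on clinical circumstances on a case-by-case basis". In that event the investigator notifies the sponsor and gives the reason.

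**Protocol 6.2.** The daily dose is made up "using the appropriate number of 25 mg and/or 100 mg film-coated tablets".

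**The concern.** The two documents do not cover the same set of doses. The protocol has a standard route with two levels and a clause that leaves room for something else. The SAPs give a rule for the standard route only. Followed as written, the rule does not leave other reductions undefined; it treats them as not being reductions.

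The dose-reduction table is the only output in either SAP that counts subjects whose dose was lowered. The adverse event summaries in section 17.1.1 cover permanent discontinuation, and in Phase II also temporary discontinuation. Neither has a row for events leading to dose reduction. For off-schedule levels the error has one direction, because such subjects can only be left out. What is at stake is a descriptive tolerability figure for the dose taken forward.

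**Working it through.** The plan states no figure to reproduce on this point, so the check compares the rules and then sizes the gap.

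**1. Which cases the rule catches (assigned dose 500 mg).**

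| Lowest dose reached | In the reduction count? | Has a minimum-dose category? |
|---|---|---|
| 300 mg or 200 mg | yes | yes |
| another level first, then 300 or 200 mg | yes | yes |
| another level only | no | no |

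For a Phase Ib subject assigned 300 mg, staying at 300 mg is no change from the planned level, so it is not a reduction. A drop to 200 mg is counted.

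**2. Size per missed subject.** The denominators are 48 (Phase II sample size) and 12 (subjects planned at the target RP2D in Phase Ib).

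- Phase II: 1/48 = 2.1 percentage points.
- Phase Ib, 12 subjects: 1/12 = 8.3 percentage points.

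**3. Range under an assumption.** Suppose 10 of 48 subjects are truly reduced (10/48 = 20.8%). This number is invented for illustration. If 0, 2, 5 or all 10 were only ever at other levels, the table would show 10/48 = 20.8%, 8/48 = 16.7%, 5/48 = 10.4% or 0/48 = 0%.

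**4. Whether other outputs show the same thing.** By the SAP formulas:

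Relative dose intensity = [cumulative dose / (weeks/3)] / planned dose per cycle.

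Cumulative dose uses actual doses: "The cumulative dose (mg) of tepotinib per subject is the sum of the actual dose levels that the subject received". Take 500 mg planned, so 500 × 21 = 10,500 mg per cycle, and 84 days on treatment, which is 12 weeks or 4 cycles. The lower doses, their start days and the 84 days are assumptions chosen only to exercise the formula.

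- 400 mg from day 22: (21 × 500 + 63 × 400)/4 = 35,700/4 = 8,925; 8,925/10,500 = 85%.
- 400 mg from day 43: (42 × 500 + 42 × 400)/4 = 9,450; 9,450/10,500 = 90%.
- 400 mg from day 64: (63 × 500 + 21 × 400)/4 = 9,975; 9,975/10,500 = 95%.
- 450 mg from day 22: (21 × 500 + 63 × 450)/4 = 9,712.5; 9,712.5/10,500 = 92.5%.

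All four lower the relative dose intensity, and none counts as a dose reduction. The deviation check PDEV38 lists subjects at 90% or less, so it catches the first two and misses the last two.

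Relative dose intensity also cannot separate a lower dose from missed doses. Missing 0.15 × 84 = 12.6 daily doses at 500 mg gives the same 85%. PDEV38 describes what it lists as a dosing error, which is not what a permitted modification is.

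**The case against.** The strongest reply is that the SAPs follow the protocol's own schedule. Protocol 6.2.3 says the two-level schedule is applied, and it withdraws subjects who cannot tolerate the lowest permitted dose, which reads like a closed set. The word recommended belongs to the guideline on triggers and rechallenge, and the case-by-case sentence qualifies that guideline. It may be about when or how to modify rather than which level. Tablet strengths show only that other doses are possible. Protocol 8.5.4 does not name a reduction count among its exposure measures, and off-schedule dosing still shows in cumulative dose, dose intensity and relative dose intensity, which the Phase II SAP also lists per subject.

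Much of this stands, and it limits the point. Three stronger readings that a reader might infer are not supported:

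- *That the protocol makes the two levels merely a recommendation.* It does not. The opening for other levels rests on the case-by-case clause alone.
- *That real reductions in general are reported as none.* Every reduction from 500 mg that reaches 300 or 200 mg is counted.
- *That unreduced subjects in the 300 mg cohort are mislabelled as reduced.* The definition requires a change from the planned level, so for them the category 'reduced to 300 mg' is simply empty.

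The reply does not close the gap. The clause speaks of modifying the dosage, which on its plain wording includes the level, and the SAPs do not say how such a case is counted. The dose-intensity summaries do not replace a count of subjects reduced, as step 4 of the working shows.

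**Conclusion.** The point holds in a narrow form and is minor. In both SAPs a subject lowered only to a dose other than 300 or 200 mg would be left out of the dose-reduction table and would have no minimum-dose category. The understatement is 2.1 percentage points per such subject among 48, or 8.3 among 12.

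This assumes that the case-by-case clause extends to the dose level and that at least one investigator uses it that way. The documents do not show that this happened or was expected, and the 10-of-48 range is illustrative only. No endpoint or test depends on the table.

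**What to change.** In section 15 of both SAPs:

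- Define a dose reduction as a change to any prescribed non-zero dose level below the subject's own assigned starting dose, as recorded on the administration eCRF page, excluding isolated missed tablets. Counting every administered dose below the assigned one would be too wide: one day short of a tablet would then appear as a tolerability reduction.
- Report the minimum prescribed dose relative to the assigned dose as 300 mg, 200 mg or 'other (specify)', with 'reduced to 300 mg' marked not applicable for subjects assigned 300 mg.

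Both SAPs refer to a planned dose level entered in the eCRF alongside the actual dose. Before programming, confirm that this field carries the currently prescribed level and not only the starting one.

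This is a reporting rule. It takes no position on which doses may be used. The cost is minor SAP wording and programming, and a reduction count that may be slightly higher.
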